10.2. Sample size

Due to the conceptual nature of this trial no formal sample size calculation has been performed. It is assumed that 25 subjects will be adequate for evaluating the sensor performance.

We strive to include an equally number of users in the categories 1pc, 2pc, flat, convex and concave.

Due to the exploratory nature of the study, drop-out subjects will not be replaced.

10.3. Level of significance and power

If a statistical analysis is performed a significance level of 5% will be applied. As this is an exploratory study no power has been applied.

10.4. Pass/fail criteria

No formal success criteria are applied in this investigation. Study results may be used for relevant claims.

The study will provide valuable insight into the performance and safety of the device and the ability to support the user with useful information regarding potential leakages in an everyday life setting.

10.5. Interim analysis

There is no planned interim analysis in this investigation that will affect the evaluation of the objectives. To facilitate and optimize the development of improved versions of the algorithm engineers working with the software will get restricted access to data before DBL. The result of their work will be for internal optimization of future versions of the algorithm only and will not be reported before after the result meeting of the study.

10.6. Statistical reason for termination of investigation

There will be no interim analysis and therefore no reason to terminate the investigation based on statistical considerations.

10.7. Deviation(s) from statistical design, method or analytical procedures

Any deviations from the statistical plan will be documented in the clinical investigation report.

11. Data management

11.1. Data collection and data management

11.1.1. Data Collection in the clinical investigation

Data will be collected through an electronic data capturing (EDC) system on electronic Case Report Form (eCRF), a secure, internet-based case report form. This system will be used to record all subject information collected in the investigation for secure data tracking and centralised data monitoring ("remote monitoring") done by monitors, as defined in the monitoring section 8

The EDC system used is [REDACTED] delivered by [REDACTED] The system is designed to be compliant with the FDA requirements of 21 CFR part 11. It is a validated data management system allowing only qualified and trained personnel to enter the system. The system has full audit trail and electronic signature.

The sponsor will be responsible for training the investigator, or delegate, in completion of the eCRF.

Principal Investigator, or delegate, at the clinical site will perform primary data collection directly into the eCRF or drawn from source-document (medical records) reviews. The eCRF will be completed on a continuous basis starting from the point of enrolling the subject to final follow up.

The eCRF will be completed by the investigator, or delegate, who have signed the Site Personnel Signature and Delegation List and Clinical Investigation Training Log. It will be the responsibility of the investigator to ensure that all measurements and observations are correctly noted in the eCRF.

All assessments and observations throughout the investigation for each subject must be carefully recorded in an eCRF or in a paper CRF (pCRF) during the visit or immediately after.

The subject will receive a smartphone with the Clinical Trial app installed. The app is developed on behalf of Coloplast A/S [REDACTED]. This Clinical Trial app is used for taking photos of used products and used during the investigation every time the subject makes a product (1pc) or baseplate (2pc) change.

11.1.2. Database Management, Queries and Quality Control

The data management system has restricted role-based access control. The principal investigator or delegate must be trained in the system prior to getting access. The training is web-based and must be completed before access to the investigation is granted. Training will be documented in the data management system. Only the principal investigator, or delegate, will be authorised to enter data in the eCRF.

The monitor, using his/her personal login information shall verify all critical data points against the source documents and issue electronic queries for the authorised clinical site personnel to respond, as defined in the monitoring plan.

The principal investigator, using his/her personal login information shall sign each eCRF.

Automated, real time access to the data enable control on study compliance and safety assessments.

A critical quality control will be performed by the sponsor's data management team and queries issued where needed. Such queries will be reviewed by the monitor and must be resolved by the site personnel.

At the end of the study a formal data review meeting will be performed before the database will be locked.

A full audit trail ensures, that each user's (site personnel, monitor, sponsor, data manager) access to and actions in the system is tracked.

The Data Management Procedures are further described in the Data Management SOPs.

11.2. Remote monitoring

Remote or centralized monitoring is a remote evaluation carried out by sponsor personnel or representatives (e.g., data management personnel, statisticians, or clinical monitors) at a location other than the site(s) at which the clinical investigation is being conducted. Remote monitoring processes can provide many of the capabilities of on-site monitoring as well as additional capabilities.

In addition to onsite monitoring visits, remote monitoring of the data entered in the eCRF system could be used to achieve the following:

- Conduct activities such as: standard checks of range, consistency, and completeness of data and checks for unusual distribution of data, such as too little variance.
- Special attention will be given in case of frequent data anomalies or errors, protocol violations or excessive dropouts.
- Augment on-site monitoring by performing monitoring activities that can only be accomplished using centralized processes (e.g., statistical analyses to identify data trends not easily detected by on-site monitoring)
- Monitor data quality through routine review of submitted data in real-time to identify missing data, inconsistent data, data outliers, and potential protocol deviations that may be indicative of systemic and/or significant errors in data collection and reporting at the site

- Verify source data remotely, provided that both source data and CRFs can be accessed remotely
- Conduct aggregate statistical analyses of study data to identify subject data that are outliers relative to others and to evaluate individual subject data for plausibility and completeness
- Conduct analyses of site characteristics, performance metrics (e.g., high screen failure rates, high frequency of eligibility violations, and delays in reporting data), and clinical data to identify early on corrective actions needed for characteristics correlated with poor performance or noncompliance

11.3. Data retention

The Investigator file must be archived for a minimum period of 10 years after the final clinical investigation report has been signed.

12. Amendments to the Clinical Investigation Plan

No changes in the clinical investigation procedures shall be affected without mutual agreement between the principal investigator and the sponsor. The agreement of the changes must be documented by signing the corresponding clinical investigation plan amendments and registered in the Change Log.

All significant changes require notification to the EC and applicable regulatory authority. Substantial changes may require approval from the EC and applicable regulatory authority prior to implementation. (Example of significant change: Changes of inclusion criteria, end points or assessment methods)

13. Deviations from the Clinical Investigation Plan

Deviations to the Clinical Investigation Plan occurs when the activities during the clinical investigation do not comply with the EC/CA approved investigation plan. A minor deviation is defined as those that don't increase risk or decrease benefit or; don't have a significant effect on the subject's rights, safety or welfare; and/or on the integrity of the data.

The investigator is not allowed to deviate from the Clinical Investigation Plan unless, under emergency circumstances or to protect the rights, safety and welfare of the subject(s).

For the purposes of this investigation, any variance from the protocol is considered a deviation and is to be reported.

The site will complete a deviation for all data-related deviations and all deviations that are not related to the data (for example, an untrained nurse performing study procedures). Deviations are reported in the Deviation Log located in the Investigator File.

If any deviations to the investigation plan are detected during the monitoring visit, the Monitor shall ensure the site reports all deviations in the eCRF or on the Deviation log in the Investigator File. Additionally, the monitor must report any deviation noted during the visit in the Periodic Monitoring Report.

Monitor will align with data management in each investigation, how data management will be informed about all deviations.

The following information about the deviation will be collected:

- Site ID, Subject ID
- Deviation Date and Investigation Visit
- Date deviation was discovered
- Clear and concise description of the event
- Provide a reason and record the corrective action taken, including the date of the corrective action. Please note corrective action can be site was re-educated on a procedure. Ensure the corrective action is documented.

- Record the EC notification date, when applicable, and retrieve a copy of the EC Submission Letter for the TMF.

13.1. Violations to the Clinical Investigation Plan

Violations to the Clinical Investigation Plan occurs when there is major deviation from the EC approved investigation plan that also increase risk or decrease benefit and/or; has a significant effect on the subject's rights, safety or welfare and/or has a significant effect on the integrity of the data.

If any violations to the investigational plan are detected, the Investigator must inform the Monitor immediately, and the Monitor will complete an investigation specific Violation Form, enter it in the investigation deviation log (eCRF or Deviation Log in the Investigator File), and inform the Clinical Manager or designee immediately.

The Monitor must report all violations detected during a monitoring visit in the Periodic Monitoring Report.

14. Device Accountability

All access to the investigational devices used in the clinical investigation is controlled by storage procedures and device accountability logs as described below. The investigational devices must only be used in this clinical investigation and only according to the CIP.

Sponsor keeps a device accountability log that states the physical location of all investigational devices from shipment of investigations devices to the investigational sites until return of or disposal.

The PI or an authorized designee keeps records documenting the receipt, use and return and disposal of the investigational devices, which includes:

- Date of receipt.
- Identification of each investigational device (batch no./serial no./unique code).
- The expire date
- The date(s) of use.
- Subject identification.
- The date on which the investigational device was returned/explanted from the subject
- The date of return unused, expired or malfunctioning investigational devices.

15. Statement of compliance

The clinical investigation is conducted in accordance to:

- Ethical principles that have their origin in the Declaration of Helsinki, 1964, Last amended at 64th WMA General Assembly, Fortaleza, Brazil, October 2013
- MDD 93/42/EEC as amended by Directive 2007/47/EC (commonly known as the Medical Device Directive).
- MDR (EU) 2017/745
- ISO 14155:2020 "Clinical Investigation of medical devices for human subjects – Good clinical practices".
- Any applicable regional or national regulations will be specified in the country specific CIP.

15.1. Ethics committee and regulatory authorities

The CIP and/or other relevant documents are submitted to the appropriate EC(s) and regulatory authorities. This clinical investigation will not begin until the required approval from the EC and regulatory authorities have been obtained. Any amendment to the protocol will be submitted to the same EC(s) and regulatory authority.

Sponsor will notify the relevant regulatory authority and EC(s) concerned of the end of the clinical investigation.

15.2. Data protection

As part of the investigation Coloplast A/S, [name] ("Coloplast") will collect and process the personal information the subject provides for the investigation ("subject personal data"). This includes identification and contact information (which may be anonymised depending on the nature of the investigation) as well as information about product usage experience and your health. Coloplast will comply with the EU General Data Protection Regulation (GDPR) and the Danish act on data protection ("databeskyttelsesloven"), including in connection with transfer of data to third countries, cf. chapter V of GDPR, Coloplast will only process the subjects' personal data:

1. To conduct the investigation and carry out related research based on subject consent (primary use), cf. articles 6(1)(a) and 9(2)(a) of GDPR,
2. To comply with applicable legal obligations to e.g. ensure reliability and safety, cf. article 6(1)(c) in conjunction with article 9(1)(i) of GDPR, and
3. If separate consent is given for secondary use of subject personal data, cf. articles 6(1)(a) and 9(2)(a) of GDPR – carry out research outside the clinical protocol to improve Coloplast's products and services, and for use in education.

Part of Coloplast's processing is carried out on third-party platforms (clinical trial databases) and certain third parties are assisting Coloplast in the processing (e.g. the investigator). Such cases will imply a transfer of your personal data to the third parties, but solely for the specified purposes and with the third parties acting on instruction from Coloplast. Data may be collected and processed across the Coloplast network, which may entail processing of personal data outside the European Economic Area. In such cases, an adequate level of protection will be ensured by the third parties being subject to the standard contractual clauses on data protection adopted by the EU or to an EU-approved certification mechanism on data protection. For further information about this please the subject can always consult Coloplast's data protection officer (details below).

Subject personal data will be kept as long as required under applicable laws and regulations. The EU Medical Device Regulation obligates Coloplast to keep the data for a period of at least ten years after the investigation is completed, or, in the event that the device is subsequently placed on the market, at least ten years after the last device has been placed on the market. Subject personal data will be deleted at the end of the mandatory retention period.

If the subject has questions or queries regarding Coloplast's handling of personal information, the subject can always contact Coloplast's Data Protection Officer at [REDACTED]. Complaints related to Coloplast's handling of subject personal information may similarly be sent to the Data Protection Officer, and the subject is also entitled to file a complaint with the relevant supervisory authority, which in the case of Denmark is the Danish Data Protection Agency (www.datatilsynet.dk).

The subject can write to [REDACTED] at any time to request:

- Access to personal data
- Correction of errors in personal data or to erase personal data
- Limit what can be done with personal data
- To receive personal data in machine-readable format (data portability).
- Withdrawal of consents the subject has given Coloplast to process personal data

15.3. Indemnity

All subjects are fully covered by Coloplast A/S insurance throughout the investigation: [REDACTED]

15.4. Financial conditions

Coloplast A/S will compensate all investigators involved in the clinical investigation for their time and resources spent on the investigation. All financial agreements with the investigation sites involved in the clinical investigation will be specified in the sponsor investigator agreement.

The expenses include the salary to the Principal Investigator and study nurses, the cost of test products, shipments, transportation and gift certificates. The Principal Investigator and study nurses have no financial interest in the investigation. The total budget for the investigation is [REDACTED] covering 25 participants, each participating in 2 test visits. The expenses are paid on an ongoing basis. All financial agreements with the investigation sites involved in the clinical investigation will be specified in a sponsor investigator agreement.

Subjects will be paid for their participation in the study and receives a gift voucher equivalent in value [REDACTED] per visit 1 and 2, in total [REDACTED] if the subject completes the investigation

If the subjects are not able to conduct remote visits and do not want a home visit, the cost of transport between Coloplast A / S and the home will be covered. Reimbursement of transport expenses are not taxable whereas payment for participation in the study is taxable per local legislations. Subjects will be paid for their participation after each visit and transport expenses will be paid in appropriate portions that justify the administration, throughout investigation period.

16. Informed consent process

Written informed consent is obtained from all subjects participating in the investigation after thorough written and verbal information. The information is given by the investigator or his/her representative in the subjects' native non-technical language. Each subject will be fully informed about the aim of the investigation, procedures, potential risks or inconveniences and/or expected benefits and have a minimum of 24h before deciding on participation, but if the subject have decided to participate in the they can sign immediately. The subjects will be informed that their participation is voluntary and that they may leave the investigation at any time, without this having any influence on their further treatment.

The informed consent signature form includes personally dated signatures of the subject and the PI or his/her representative responsible for conducting the informed consent process. A copy will be provided to the subject. The signature can be either in handwriting or by using an electronic signature form like DocuSign.

If new information is to be given during the investigation, sponsor will inform the investigators, and the new information is given to the subjects by the investigator. If new information becomes available that can significantly affect a subject's future health and medical care that information will be provided to the subject in written form. CM is responsible for writing the information and providing it to investigators that will further provide it to the subjects. If applicable, all affected subjects shall be asked to confirm their continuing informed consent in writing.

This procedure also applies to informed consent obtained from a subject's legal representative. The procedure cannot waive the subjects' legal rights.

17. Subject compensation

17.1. Compensation in case of injury

Subjects will be covered through Coloplast insurance see 15.3

17.2. Compensation for participating in the clinical investigation

Subjects will be compensated as described under Financial conditions 15.4

18. Adverse events, adverse device effects and device deficiencies

18.1. Adverse events

An adverse event is any untoward medical occurrence, unintended disease or injury, or untoward clinical signs (including abnormal laboratory findings) in subjects, users or other parties, whether or not related to the medical device(s), or the procedures involved. This could include events such as headache or dizziness.

18.2. Adverse device effect

An adverse event, which is related to the use of the investigational medical device, is an adverse device effect, and should be marked as related or possibly related on the adverse event form.

The definition of an adverse device effect includes any event resulting from insufficiencies or inadequacies in the instruction for use, deployment, implantation, installation and operation, or any malfunction of the medical device, as well as any event resulting from use error or from intentional misuse of the device.

Table 2 lists anticipated adverse device effects that may occur.

Table 2 Anticipated adverse device effects and their likely incidence rates

ANTICIPATED ADE	INCIDENCE RATE
Peristomal skin irritation (incl. mechanical trauma)	< 10%
Allergic peristomal skin irritation (dermatitis)	< 1%

18.3. Device deficiency

A device deficiency is the inadequacy of the investigational medical device or comparator with respect to its identity, quality, durability, reliability, safety or performance. This includes malfunctions, use errors and inadequacy in the information supplied by the manufacturer including labelling.

Example: Transmitter not able to charge.

18.4. Serious adverse events (SAE)

A serious adverse event is an adverse event that:

- Led to death,
- Led to a serious deterioration in the health of the subject, users or other persons as defined by one or more of the following:
 1. a life-threatening illness or injury, or
 2. a permanent impairment of a body structure or a body function including chronic diseases, or
 3. in-patient or prolonged hospitalization, or
 4. medical or surgical intervention to prevent life-threatening illness or injury or permanent impairment to a body structure or a body function.
- Led to fetal distress, fetal death or a congenital abnormality or birth defect.

This includes device deficiencies that might have led to a serious adverse event if:

- Suitable action had not been taken, or
- Intervention had not been made, or
- Circumstances had been less fortunate.

These are handled under the serious adverse event reporting.

Planned hospitalization for a pre-existing condition, or a procedure required by the CIP, without serious deterioration in health, is not considered a serious adverse event.

18.4.1. Serious adverse device effect (SADE)

A serious adverse device effect is an adverse device effect that has resulted in any of the consequences characteristic of a serious adverse event.

18.4.2. Anticipated serious adverse device effect (ASADE)

Anticipated serious adverse device effect is any event that by its nature, incidence, severity or outcome has been previously identified in the risk analysis report. In this investigation no SADE are anticipated.

18.4.3. Unanticipated serious adverse device effect (USADE)

An unanticipated serious adverse device effect is a serious adverse device effect which by its nature, incidence, severity or outcome has not been identified in the current version of the risk analysis report.

18.5. Medical care of subjects

Principal investigator shall ensure that adequate medical care is provided to a subject experiencing an adverse event during and after participation in the clinical investigation. All serious adverse events will be followed until a resolution is addressed.

The current status of all ongoing adverse events is documented during site close-out.

18.6. Reporting and timelines

18.7. Investigator's reporting responsibilities

- PI at each site must assess all (S)AE's that occur at his/her site.
- All serious adverse events and serious adverse device effects must be reported to sponsor within 24 hours of the site becoming aware of the event.
- A device deficiency that could have led to a serious adverse event but did not because suitable action was taken, intervention had been made or because of fortunate circumstances should be reported to sponsor within 24 hours of the site becoming aware of the event.
- New findings and/or updates in relation to already reported serious events should also be reported to sponsor within 24 hours of the site becoming aware of the event.
- Device deficiencies and all adverse device effects must be reported to sponsor within 10 days of becoming aware of the event.

When reporting the SAE, the relationship to the test material shall be described whether the event is considered

- **Not related**, the event has no temporal relationship with the use of the test material or the procedures.
- **Unlikely related**, the relationship with the use of the test material seems not relevant and/or the event can be reasonably explained by another cause, but additional information may be obtained.
- **Possibly related**, the relationship with the use of the test material is weak but cannot be ruled out completely. Alternative causes are also possible (e.g. an underlying or concurrent illness/ clinical condition or/and an effect of another device, drug or treatment). Cases were relatedness cannot be assessed or no information has been obtained should also be classified as possible.
- **Probably related**, the relationship with the use of the test material seems relevant and/or the event cannot reasonably be explained by another cause, but additional information may be obtained.
- **Definitely related/Causal relationship**, the event has a temporal relationship with the test material use/application or procedures.

All above events must be reported by use of the relevant adverse event/serious adverse event/device deficiency form.

Please report to:

██████████ and ██████████

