4.6. Total number of devices intended for the clinical investigation

Subjects will be delivered one test product per day and 6 extras. Subjects will be delivered a starter box and retail boxes with sensor layers (10 in a box)

Each subject will be supplied with test products and study supplies as described below:

- 1 phone (iPhone or Android) with a specially designed application installed
- 1 charger
- 1 charging cable
- 1 charging adapter
- Two transmitters
- Test products to support a daily change pattern + 6 extra
- One iPhone for the Clinical Trial App

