5.1. General

An open-labelled, single arm study design was chosen for this study.

Study duration: 21 days + 3 days.

Study visits will be conducted remotely via video calls/phone calls if technical possible. If considered necessary by the study nurse, the visits can take place either in subjects own home or at a test facility at Coloplast.

V0: Inclusion

V1: Baseline demographics & evaluation (questionnaire) & Introduction to test product, start test period.

V2: Termination

Vx: Follow up visits if needed

21 days are considered sufficient to meet endpoints of performance of the sensor layer, user experience with test product and to observe trends in changes of quality of life. The visit window of 3 days is chosen for flexibility purposes.

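### For serious adverse events during device use, the top and bottom relatedness grades in section 18.7 rest on timing alone, so the grades overlap and an incidental event can be labelled a serious device effect

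*Combined protocol and SAP*

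**What the plan says.** Section 18.7 introduces its five-grade scale with "When reporting the SAE, the relationship to the test material shall be described whether the event is considered". The grades run as follows.

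- *Not related*: "the event has no temporal relationship with the use of the test material or the procedures".
- *Unlikely related*: the relationship "seems not relevant and/or the event can be reasonably explained by another cause, but additional information may be obtained".
- *Possibly related*: the link is weak but not excluded, and other causes may also be present. Cases that cannot be assessed go here too.
- *Probably related*: the relationship "seems relevant and/or the event cannot reasonably be explained by another cause, but additional information may be obtained".
- At the top of the scale, *Definitely related/Causal relationship*: "the event has a temporal relationship with the test material use/application or procedures".

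No other section adds a criterion to the first or the last grade.

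Section 18.2 uses different terms. An adverse event related to use of the device is an adverse device effect and "should be marked as related or possibly related on the adverse event form". Section 18.4.1 makes an adverse device effect with serious consequences a serious adverse device effect (SADE). Section 18.4.3 makes a SADE not identified in the risk analysis report an unanticipated one (USADE). Section 18.4.2 states that no SADE is anticipated.

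On exposure, section 5.1 gives "Study duration: 21 days + 3 days" and section 4.6 gives "Subjects will be delivered one test product per day and 6 extras".

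**The concern.** A causality scale should rise from no plausible link to a link that is established. Here the three middle grades use relevance and alternative causes, while the two end grades use only timing. Timing separates little when the product is in use for most of the observation period, because almost any event in that period coincides with use.

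The study has no comparator, so the investigator's attribution is the main means of separating device effects from background illness. If the scale can place an incidental hospital admission in its highest grade, the SADE and USADE counts no longer mean what their names say. Section 10.4 expects the study to give insight into the safety of the device, and those counts are part of that evidence.

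**Working it through.** The plan gives no figure to reproduce. The check is to apply the wording to defined cases.

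**1. An SAE during wear with a clear other cause**

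| Grade | What the wording tests | Is it met? |
|---|---|---|
| Not related | Timing absent | No: the event falls during use |
| Unlikely related | Link seems irrelevant, and/or another reasonable cause | Yes |
| Possibly related | Weak link not excluded; other causes allowed | Yes, if the link cannot be wholly excluded |
| Probably related | Link seems relevant, and/or no other reasonable cause | No, unless the link is thought relevant |
| Definitely related | Timing present | Yes |

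The event fits the second and fifth grades together, possibly the third as well, and is barred from the first.

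**2. Order of the grades.** In an ordered scale, an event that satisfies the top grade should be at least as strong a case as one in the grade below. The event in step 1 fails *Probably related* and meets *Definitely related*. The top grade is therefore the easier of the two to reach.

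**3. An SAE before first use.** Enrolment is at consent (section 6.4), the product is introduced at Visit 1 (section 7.1.1), and adverse events are registered from screening (section 7.2). Visits 0 and 1 may be combined, so only some subjects have a pre-use interval. An event in that interval, not timed to a study procedure, has no temporal relationship and can be *Not related*. The defect is confined to events during use.

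**4. Route into the safety summary.** *Definitely related* makes the SAE an adverse device effect (18.2), hence a SADE (18.4.1), and a USADE unless the risk analysis report identifies it (18.4.3). With no SADE anticipated, one incidental SAE graded by the literal rule gives 0 + 1 = 1 SADE.

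**5. Route into expedited reporting.** Section 18.7 sends every SAE to the sponsor within 24 hours, and section 18.8 sends every SAE to authorities and ethics committees within 7 calendar days. Neither step depends on the grade.

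**6. Agreement with section 18.2.** That section has two labels and section 18.7 has five grades. The label *related* can naturally be taken to include probable and definite, but neither section says so or says which grades make an event an adverse device effect. The adverse event form is not in the documents, so its categories cannot be checked.

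**The case against.** The strongest reply is that no experienced investigator would grade this way. The top grade carries the label *Causal relationship*, *Unlikely related* is available for an event with another explanation, and temporal relationship may be meant as a plausible time course rather than coincidence. There is one site and 25 subjects, so few people will apply the scale, and all SAEs are reported anyway. Much of this stands. The overlap makes grading ambiguous and does not force the top grade, and no reporting obligation is missed. But a label does not replace a criterion. A plausible time course still excludes no other cause. An assessor using good judgement still may not use *Not related* for an on-wear event, however unconnected it is.

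A reader might infer more than the documents support:

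- *That every adverse event becomes definitely related.* The scale is introduced for SAEs. A non-serious headache, the type of event section 18.1 gives as an example, is not sent through it by the text.
- *That no event can be Not related, or that all on-wear events must be Definite.* Step 3 answers the first. The overlap in step 1 answers the second, since another grade is also open.
- *That each misgraded event moves a rate by 1/25 = 4 percentage points against Table 2.* Table 2 lists two specific skin effects, which an unrelated SAE does not alter, and the plan makes no comparison with it.
- *That section 18.2 excludes probably related events.* The natural reading of *related* includes them. What is missing is a statement of the mapping.

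**Conclusion.** The definitions are wrong as written, within a limited scope. For an SAE while the device is in use, section 18.7 literally supports *Definitely related*, rules out *Not related*, and may also support *Unlikely related*. The top grade is less demanding than the one below it.

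The consequence is possible misclassification as a SADE or USADE, and a distorted safety summary in a single-arm study. It does not reach expedited SAE reporting or any efficacy or performance endpoint. No rate can be attached to it, because the documents give no expected number of SAEs. The scale of effect is one SADE for each incidental SAE graded literally, where none is anticipated.

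The conclusion assumes that temporal relationship includes occurrence during use, a term the plan does not define. It also assumes that the device is worn for most of the test period; the daily supply implies this but no rule states it. Less wear would reduce the number of events affected and leave the wording defect in place.

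**What to change.** In section 18.7:

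- Require for *Definitely related* both a temporal relationship and no other reasonable explanation.
- Let *Not related* also cover events clearly due to another cause, even if they occur during use.
- Check the middle grades against the new ends. The and/or wording in *Unlikely related* and *Probably related* lets one event meet both, or meet *Probably related* and the revised top grade together. Either replace it or state that a middle grade applies only when neither end grade is met, with a rule for choosing between middle grades.

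In section 18.2, or by cross-reference from it, state which of the five grades count as device-related, so that the adverse event form, the adverse device effect definition and the SADE/USADE definitions use one rule.

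Using the five grades for all adverse events would be tidy but is optional; the correction does not depend on it.

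The cost is wording in two sections, any matching change to the form, and a short note to the site. It needs no new data, visits or subjects. Any SAE already graded under the present wording should be regraded.
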